#### 7.5.2 Preservation of BCNVA

The analysis of this clinical outcome will be based on the observed data of IOPCL AMD-MAG. The number and percent of IOPCL implanted eyes with a BCNVA loss of 2 or more lines (≥10 letters) at 12 months from preoperative will be derived.

Additionally, if needed, data listing or summary will be provided for eyes with a BCNVA loss of  $\geq 2$  lines from the best BCNVA before the corresponding visits.

# 7.5.3 Secondary Surgical Intervention (SSI)

For each SSI category, the cumulative number and percent of eyes reported with the SSI will be reported. A line listing will be reported for each SSI which will included subject ID, visit, visit date, SSI category, and clinical sequalae.

# 7.5.4 Successful Delivery of the IOPCL

The analysis of this clinical outcome will be based on the observed data of IOPCL AMD-MAG IOPCL. The number and percent of eyes with successful delivery of the IOPCL will be reported.

# 7.5.5 Long-term Adherence and Positional Stability

The analysis of this clinical outcome will be based on the observed data of IOPCL AMD-MAG IOPCL. The number and percent of eyes with established and maintained central spacing as determined by UBM imaging between the IOPCL and IOL will be reported. The number and percent of eyes reporting decentration of the IOPCL or tilt of the PCIOL and/or IOPCL will be reported.

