4.1. Safety Endpoints

- Preservation of BCDVA Proportion of eyes (< 5%) that lose two or more lines of BCDVA (≥10 letters on the ETDRS chart) at 12 months from baseline.
- Preservation of BCNVA Proportion of eyes (<5%) that lose two or more lines of BCNVA
 (≥10 letters on the Sloan Near Vision Chart at 14 cm) at 12 months from baseline.
- Incidence of secondary surgical intervention (SSI).
- Successful delivery of the IOPCL AMD-MAG as determined at all postoperative scheduled visits starting at 7-14 days post-operative.
 - No capsular tear
 - No visible damage to either the PCIOL or the IOPCL AMD MAG
 - o Uniform leaflet coverage of all IOPCL AMD MAG haptic tabs
- Long-term adherence and positional stability
 - O Gap: Minimal change in uniformity of the gap between consecutive scheduled visits at 1-2 months and later as determined by UBM measurements. Minimal change is defined as +/- 10 microns between visits is established and maintained using UBM imaging.
 - o Tilt:
- Tilt of the PCIOL as determined at all post-operative scheduled visits starting at 30-60 days post-operative. Minimal tilt of the PCIOL confirmed via penlight examination and defined as ≤ 10 degrees between the postoperative tilt of the PCIOL and the pre-operative tilt of the PCIOL.
- Tilt of the IOPCL AMD-MAG as determined at all post-operative scheduled visits starting at 30-60 days post-operative. Minimal tilt of the IOPCL AMD-MAG (using the PCIOL as a reference point) confirmed via penlight examination and defined as ≤ 10 degrees between the post-operative tilt of the. PCIOL and the postoperative tilt of the IOPCL AMD-MAG.
- O Decentration: Decentration as determined at all post-operative scheduled visits starting at 7-14 days post-operative. Centration of the IOPCL AMD-MAG (using the PCIOL as a reference point) confirmed during slit lamp examination and defined as uniform exposed area of the PCIOL outside of the IOPCL AMD-MAG at the vertical and horizontal meridians between ≥ 0.25 mm and ≤ 0.75 mm.
- Counts and percentages for incidence of cumulative and persistent intraoperative and post-operative adverse events
- Counts and percentages for incidence of secondary surgical interventions (e.g., removal
 of interlenticular opacity, repositioning of IOPCL, explant of IOPCL, repositioning of
 PCIOL) (excluding Nd:YAG treatments for PCO).

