12.1.6. Removing Cellular Matter (Opacification) between the PCIOL and IOPCL

Removal of cellular matter (opacification) between the PCIOL and IOPCL will be recorded. **Prior to recording, please ensure that the video equipment is in full working order**. Video recordings will be shared with the Sponsor and FDA.

Using an irrigating cannula and BSS loosen the cortical/cellular material between the two lenses from the periphery, followed by removal with a coaxial/aspiration (I/A handpiece). Alternatively utilize a bi-manual I/A system with separate irrigation and aspiration handpieces. These small handpieces can be introduced through two 1.0 mm paracentesis incisions and can easily fit between the two lenses delivering irrigation from one side and aspiration from the opposite side to remove any cortical or inter-lenticular cellular material place a small amount of ProVisc® within the angle of the anterior chamber to stabilize the chamber while allowing for free flow of BSS fluid. Use a straight 27-gauge cannula on a 5cc syringe filled with BSS to vigorously irrigate the space between the two lenses. If for some reason the vigorous irrigation did not remove all the debris from the inter-lenticular space carefully release the haptic/tabs of the IOPCL closest to the location of the debris and continue to irrigate. If this approach is unsuccessful consider removing the IOPCL, irrigate the surface debris on the surface of the PCIOL and replace it with another IOPCL. If the debris attached to the surface of the PCIOL remains adhered after the final attempt to irrigate do not introduce a new IOPCL. At the conclusion of the case, please record in detail on the CRF every and all steps taken to remove the cellular material between the two lenses.

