16.3. Postoperative Ocular Adverse Events

Endophthalmitis

- Toxic Anterior Segment Syndrome (TASS)
- Chronic Anterior Uveitis
- Hyphema
- Hypopyon
- Implantable Pseudophakic Contact Lens Dislocation
- Cystoid Macular Edema
 - Clinically Significant Cystoid Macular Edema with reduction in BCDVA of 20/40 or worse at Form 3 (1-2 months post op) or later
- Pupillary Block
- Mechanical Pupillary Block
- Retinal Detachment
 - Rhegmatogenous Retinal Detachment
- Malpositioned/Misaligned Optics (IOPCL not centered over PCIOL and with unequal leaflet coverage of all IOPCL haptic tabs, or IOPCL tilted away from the PCIOL and without anterior leaflet coverage)
 - Early onset: occurring prior to Form 4 visit window (i.e., < 120 days)
 - o Late onset: occurring \ge 120 days
- Unseated IOPCL haptic tabs (One or more haptic tabs not securely attached to the PCIOL)
- Lens Optical Performance
- Mechanical Failure (Tear in haptic tab)
- Vitreous Aspiration for Pupillary Block
- Corneal Stroma Edema
 - o Corneal Edema with BCDVA of 20/40 or worse at Form 3 (1-2M post-op) or later
- Iritis present at 1-month or later
- Macular Edema present at 1-month or later
- Raised IOP requiring treatment
 - o Raised IOP, greater than 10 mmHg above baseline or greater than or equal to 25 mmHg.
- Iris Chafing
- Iris Trauma
- Iris Transillumination Defects

- Pigment Dispersion
- Pseudophacodonesis or Evidence of Zonular Trauma/Dehiscence
- Inter-device opacification or fibrosis between the PCIOL and IOPCL
- Ruptured capsular tissue
- Patient Reported Symptoms described as severe.
- Inability to go down steps, stairs or curbs in dim light or at night due to postoperative vision
- Inability to notice objects in the periphery while walking due to postoperative vision
- Other

Note: Secondary Surgical Intervention(s) (SSI) may be necessary to resolve any of the adverse events identified above. If an SSI is conducted in the trial, the details of the SSI and corresponding reason for SSI will be documented on the SSI CRF.

Examples of Secondary Surgical Interventions

- Irrigation of IOPCL/PCIOL Interface
- IOPCL Exchange
- Reposition of the same Implantable Pseudophakic Contact Lens
- IOPCL Removal
- Iridectomy for Pupillary Block

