## 2 STUDY OBJECTIVE

The primary objective of this study is to determine the stability of the IOPCL AMD-MAG to successfully adhere to a pseudophakic intraocular lens without rotation or slippage.

The secondary objective of this study is to determine if the IOPCL-AMD-MAG can improve uncorrected near visual acuity in subjects previously implanted with an Alcon SN60WF, SA60AT or SA60WF monofocal intraocular lens.

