# 6.2 Sample Size

Sample size is limited to maximum of 10 subjects (eyes) for this Early Feasibility Study (EFS).

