#### 6.4 Data Transformations and Derivations

- Age in years (round down) will be calculated using informed consent date and birth date.
- Time variables based on two dates (e.g., Start Date and End Date), will be calculated as (End Date Start Date) (in days) unless otherwise specified in the planned analysis section. For example, the postoperative day = postoperative visit date lens implantation date (i.e. surgical date).
- The following unit conversion will be implemented unless otherwise specified:
  - $\circ$  Months = Days / 30.4375
  - $\circ$  Years = Days / 365.25

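### An eye whose lens slips and is surgically repositioned between scheduled visits can be counted as stable, because the stability count is not linked to secondary surgical interventions or interim findings

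*SAP*

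**What the plan says.** - **Objective.** SAP 2 gives the primary objective as to "determine the stability of the IOPCL AMD-MAG to successfully adhere to a pseudophakic intraocular lens without rotation or slippage". Protocol 4 says the same.
- **Definition.** Protocol 4.1 defines the gap criterion as "Minimal change in uniformity of the gap between consecutive scheduled visits at 1-2 months and later as determined by UBM measurements", with a tolerance of ±10 microns; SAP 3.2 repeats it. Tilt (limit 10 degrees) is judged at scheduled visits from 30-60 days. Centration (0.25 to 0.75 mm of exposed PCIOL) is judged at scheduled visits from 7-14 days.
- **Analysis.** SAP 7.5.5 works on observed data and reports "The number and percent of eyes with established and maintained central spacing as determined by UBM imaging". It adds a count of eyes with decentration or tilt. SAP 6.5 uses available data without imputation.
- **Measurement.** Protocol 15 schedules UBM at 30-60, 120-180 and 330-420 days and lists it for interim visits. IOPCL location is recorded at all scheduled postoperative visits and at interim visits. Neither has a post-removal line.
- **Interventions.** The SSI examples in Protocol 16.3 include "Reposition of the same Implantable Pseudophakic Contact Lens", exchange and removal, and the reason goes on the SSI case report form. Protocol 12.1.6 allows the surgeon, when debris between the lenses cannot be cleared, to remove the IOPCL and "replace it with another IOPCL".
- **Separate outputs.** SAP 7.5.3 gives cumulative SSI counts and a line listing. SAP 7.5.6 gives adverse events by visit and cumulatively. Neither section refers to the stability count.

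**The concern.** The objective asks whether the lens can "successfully adhere to a pseudophakic intraocular lens without rotation or slippage". A lens that lost position and had to be put back surgically has answered no. The written criterion does not ask that question. It asks whether two scheduled readings agree. If the slip and the repair both fall between those readings, or both come before the first UBM, the gap criterion has nothing to detect. The tilt and centration criteria look only at the scheduled visits on either side.

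At stake is the headline figure for the primary objective. One table could report every eye as maintained while another lists a repositioning. No rule says how the two combine, so whoever reconciles them would choose that rule after seeing the outcomes.

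**Working it through.** The plan gives no expected stability rate, SSI rate, success threshold for stability, or power calculation, so there is no figure to reproduce. The check has three parts.

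**1. Time between scheduled gap readings** (windows from Protocol 15)
- First to second UBM: shortest 120 − 60 = 60 days, longest 180 − 30 = 150 days.
- Second to third UBM: shortest 330 − 180 = 150 days, longest 420 − 120 = 300 days.
- Before 30-60 days there is no scheduled UBM. Location and slit lamp are examined at 1-2 and 7-14 days, so only the gap measure is blind in that period.

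**2. Following the written rule for one eye**
- The lens slips after the first UBM, is found at an interim visit and is repositioned before the second UBM.
- If the two scheduled readings differ by 10 microns or less, the eye meets the gap criterion. If tilt and centration are within limits at the scheduled visits, it meets those too. The interim reading is collected but is not part of the definition.
- If the readings differ by more than 10 microns, the eye already fails.
- If the lens is explanted for loss of position, the post-removal schedule lists no UBM. On observed data the eye may have no value and leave the denominator.

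**3. Size**

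Input from the documents: n = 10, the maximum in SAP 6.2. Assumptions, because the documents give no rates: k eyes are repositioned for loss of position, m of them re-measure within tolerance, and all other eyes are stable.
- As written: (n − k + m)/n
- Repositioning scored as failure: (n − k)/n
- Difference: m/n, or 10 percentage points per eye when n = 10

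Brackets show exact (Clopper-Pearson) 95% intervals.

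| k | m | As written | Scored as failure | Difference |
|---|---|---|---|---|
| 0 | 0 | 10/10 = 100% (69.2-100) | 10/10 = 100% (69.2-100) | 0 |
| 1 | 0 | 9/10 = 90% (55.5-99.7) | 9/10 = 90% (55.5-99.7) | 0 |
| 1 | 1 | 10/10 = 100% (69.2-100) | 9/10 = 90% (55.5-99.7) | 10 points |
| 2 | 1 | 9/10 = 90% (55.5-99.7) | 8/10 = 80% (44.4-97.5) | 10 points |
| 2 | 2 | 10/10 = 100% (69.2-100) | 8/10 = 80% (44.4-97.5) | 20 points |
| 3 | 3 | 10/10 = 100% (69.2-100) | 7/10 = 70% (34.8-93.3) | 30 points |

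If the k eyes are explanted for loss of position and leave the denominator, the comparison is (n − k)/(n − k) against (n − k)/n: 9/9 = 100% against 90%, 8/8 = 100% against 80%, or 7/7 = 100% against 70%.

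**The case against.** The strongest reply is that nothing is hidden. SSI incidence is itself a safety endpoint, with a listing by subject and visit. Malpositioned optics and unseated haptic tabs are listed adverse events, reported cumulatively. The SAP 7.5.5 sentence on decentration and tilt names no visit, so it could be read to include interim findings. With at most 10 eyes, descriptive summaries and no success threshold for stability, a reader could reconcile each case by hand. This stands as far as visibility goes. It does not correct the percentage reported for the primary objective, and the SSI listing in SAP 7.5.3 does not name the reason for the intervention among its items.

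A reader might also infer more than the documents support:
- *That a repositioned eye always counts as stable, so the rate is biased.* No section says so. The eye counts only if its scheduled readings happen to agree, and with no such eye there is no effect.
- *That an exchanged eye is scored by comparing the first lens with the second.* Exchange involves removal, and the plan does not say whether the eye moves to the post-removal schedule, restarts or continues. It could be counted, restarted or dropped.
- *That any error favours the device.* The replacement in Protocol 12.1.6 is for debris. If the first lens never moved and the second sits more than 10 microns differently, comparing the two would score the eye unstable, against the device.
- *That one exchanged eye could decide the primary effectiveness result around its 75% mark.* This needs an invented scenario. Using the observed 12-month acuity of a re-operated eye is also a legitimate choice for an endpoint defined as a proportion of eyes.

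**Conclusion.** The concern holds as a defect in the stability rule. Applied exactly as written, the rule can class an eye as maintained although its lens slipped and was surgically repositioned, and it may drop an eye explanted for loss of position. For eyes treated for loss of position, the effect on the rate is zero or upward. With 10 eyes it is 10 points for each repositioned eye that re-measures within tolerance: 100% against 90%, 80% or 70% for one, two or three such eyes. These counts are assumptions.

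The documents do not establish that the bias will occur, that it must favour the device when lenses are exchanged, or that the effectiveness result is affected.

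The rule should be settled before the 4-6 month interim analysis. SAP 4 ties an IDE submission to outcomes at that point, when only one scheduled gap comparison exists. Under SAP 1, a rule chosen from the data would have to be reported as post hoc.

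**What to change.** In SAP 7.5.5 and Protocol 4.1:
- State that an eye is not maintained if the IOPCL is repositioned, exchanged or removed for loss of position, with the reason taken from the SSI case report form. The same applies to an interim-visit finding beyond the stated gap, tilt or centration limits. The eye stays in the denominator whatever its later scheduled values.
- For exchange or removal for other reasons, such as interlenticular opacity or intolerance, assess stability on the first lens up to that date. Compute no gap change across two lenses, and list any available second-lens data separately.

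In SAP 6.4, count postoperative day from the first implantation.

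Optionally, in SAP 7.4.1 and 7.4.2, add a supplementary line with exchanged or repositioned eyes counted as non-responders, beside the as-observed proportion.

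The cost is analysis wording plus an endpoint statement in the protocol. The first-lens rule uses SSI, reason, UBM and location data that are already collected. Second-lens data are listed only where available, since the plan does not clearly schedule UBM after an exchange. The downside is that the reported stability rate may be lower. The change concerns scoring only and does not alter clinical management.

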## 7.5.6 Adverse Events

For each adverse event, number and percent of eyes reported with the event will be summarized at each scheduled visit (including intraoperatively) and during the study (i.e. cumulative and persistent).

## 7.5.7 Other Safety Analyses

## 7.5.7.1 Best-corrected Distance Visual Acuity

All the available monocular best-corrected distance visual acuity at each protocol specified scheduled visit will be presented for the implanted eyes. The categorical presentations will include the visual acuity of 20/16 or better, 20/20 or better, 20/25 or better, 20/32 or better, 20/40 or better, 20/50 or better, 20/63 or better, 20/80 or better, and worse than 20/80.

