5.1. Inclusion Criteria

- 1. Subjects aged 55 years or older.
- 2. Subjects who have already had cataract surgery with an Alcon SN60WF, SA60AT or SA60WF monofocal intraocular lens with a lens power between 17.0 diopters and 24.0 diopters clearly evidenced by photographic documentation by one of the following:
 - patient medical record
 - clinic chart with labeling attached
 - surgical record with labeling attached, or
 - patient identification card with make, model and serial number.
- 3. Subjects who have already had cataract surgery at least 6 months from the planned date of the IOPCL surgery.
- 4. Subjects with non-neovascular dry AMD or stable wet AMD meeting the following criteria:
 - No macular fluid retention in the past 12 months
 - No treatment within the past 12 months
 - No change in Amsler Grid test within the past 12 months
 - No subretinal fluid or macular hemorrhage confirmed by optical coherence tomography (OCT) imaging.
 - No fundoscopic changes within the past 12 months (i.e., changes in retinal pigment epithelium).
- 5. Subjects with best corrected distance visual acuity from 20/80 to 20/800.
- 6. Subjects with a preoperative manifest refraction spherical equivalent (MRSE) of +1.0D to -1.0D.
- 7. Subjects with ≤1.0D of corneal cylinder determined by keratometry readings.
- 8. Subjects who are unsatisfied with their current near vision correction provided by either spectacles or external magnifier.
- 9. Subjects who have experienced and failed one or more high-magnification refractive correction alternatives to the IOPCL AMD-MAG.

- 10. Subjects who demonstrate at least 10 letters of near visual acuity improvement with the simulation/tolerance test (using manifest refraction with +7.0D add) compared to conventional near vision testing (using manifest refraction with +3.0D add).
- 11. Subjects with a minimum endothelial cell count of 1800 cells/mm².
- 12. Subjects willing to abstain from pursuing any other surgical vision-correcting procedures for the duration of the study.
- 13. Subjects who are willing and able to complete all required postoperative visits.
- 14. Subjects who are able to comprehend and sign a statement of informed consent.

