## 7.5.1 Preservation of BCDVA

The analysis of this clinical outcome will be based on the observed data of IOPCL AMD-MAG. The number and percent of IOPCL implanted eyes with a BCDVA loss of 2 or more lines (≥10 letters) at 12 months from preoperative will be derived.

Additionally, if needed, data listing or summary will be provided for eyes with a BCDVA loss of  $\geq 2$  lines from the best BCDVA before the corresponding visits.

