## **7.5.7.4 Tonometry**

Goldmann measurements of IOP and its change from baseline will be summarized descriptively at each visit.

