#### 7.5.7.6 Contrast Sensitivity (Mesopic)

Mesopic contrast sensitivity and its change from baseline will be summarized descriptively at each visit.

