# 7.5.7.8 Specular Microscopy

Endothelial cell count and its change from baseline will be summarized descriptively at each visit.

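### By-visit BCDVA bins stop at the best entry acuity and no change from preoperative is committed before 12 months; separately, the exploratory reading criterion as worded rewards slower reading

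*SAP*

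**What the plan says.** **Distance acuity.** Protocol 5.1, criterion 5, admits "Subjects with best corrected distance visual acuity from 20/80 to 20/800". SAP 7.5.7.1 presents BCDVA at each scheduled visit in nine categories, from 20/16 upwards in denominator, ending "20/63 or better, 20/80 or better, and worse than 20/80". The first BCDVA safety endpoint in Protocol 4.1 is "Proportion of eyes (< 5%) that lose two or more lines of BCDVA" at 12 months, with two lines equated to 10 ETDRS letters. SAP 7.5.1 implements it as a count of eyes with "BCDVA loss of 2 or more lines (≥10 letters) at 12 months from preoperative will be derived". The same section continues: "Additionally, if needed, data listing or summary will be provided for eyes with a BCDVA loss" of two or more lines, measured from the best BCDVA before the visit in question.

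Other safety measures are handled differently:
- SAP 7.5.7.4: "Goldmann measurements of IOP and its change from baseline will be summarized descriptively at each visit".
- SAP 7.5.7.6: "Mesopic contrast sensitivity and its change from baseline will be summarized descriptively at each visit".
- SAP 7.5.7.8: "Endothelial cell count and its change from baseline will be summarized descriptively at each visit".

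SAP 7.4.2 also sets letter-change bins for near acuity. BCDVA has neither. SAP 6.8 plans an interim analysis at the 4-6 month visit without listing its tables, and SAP 4 ties an IDE application to outcomes at that visit.

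**Reading.** Protocol 4.5 and SAP 3.1.3 and 7.4.3 define improved reading speed by three things together: a gain of at least two lines or blocks, a fall of at least 1 minute in reading speed, and a better critical point size. SAP 7.4.3 then bins the change in reading rate as gains and losses in minutes.

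**The concern.** A by-visit acuity table should show an eye that has got worse. Here the last cut-point equals the best acuity at which an eye can enter. Seven of the nine categories are better than any eligible entry acuity, and nearly all of the entry range lies in one open bin. In a study of at most 10 eyes, change in a single eye is the safety information, and before 12 months no table or listing of that change is firmly committed.

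The reading criterion has a different fault: its direction. Minutes measure time, not speed. Taken literally, an eye that gains two blocks, improves its critical point size and reads faster fails, while one that meets the same two conditions and reads slower succeeds. The minute bins do not say whether a gain is good or bad.

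**Working it through.** The plan states no figure for either point, so there is none to reproduce.

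**Inputs.** Entry range 20/80 to 20/800 (Protocol 5.1). Bins (SAP 7.5.7.1). Two lines = 10 letters and the 5% level (Protocol 4.1). At most 10 eyes (SAP 6.2). Assumption: one line = 0.1 logMAR, the usual ETDRS step.

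**Width of the entry range.** logMAR = log10(denominator/20). 20/80 gives 0.602 and 20/800 gives 1.602. At 5 letters per 0.1 logMAR, the range is 50 × (1.602 − 0.602) = 50 letters, or 10 lines. The levels are 20/80, 100, 125, 160, 200, 250, 320, 400, 500, 640 and 800, which is 11. Only 20/80 lies above the open bin; the other 10 start in it.

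**Effect of a two-line loss on the bin.** 20/80 falls to about 20/127 and changes bin. 20/100 falls to about 20/158, 20/200 to about 20/317 and 20/400 to about 20/634; none changes bin. The documents give no baseline distribution. The share of two-line losses visible in the bins therefore runs from 0% (no losing eye entered at 20/80) to 100% (all did).

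**One eye against the 5% level.** 1/10 = 10%. A single eye is below 5% only when n is 21 or more, so with at most 10 eyes the level is met only by zero losses.

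**Do the general descriptive statistics (SAP 6.1) fill the gap?** Assume ten eyes, one per line from 20/80 to 20/640. In letters relative to 20/80 these are 0, −5, ..., −45: mean −22.5, median −22.5, SD 15.1, minimum −45, maximum 0. Move each eye down 10 letters in turn:

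| Eye that loses 10 letters | Before → after | Bin | Median | Minimum | Maximum |
|---|---|---|---|---|---|
| 20/80 | 0 → −10 | changes | −22.5 | −45 | **−5** |
| 20/100 | −5 → −15 | same | −22.5 | −45 | 0 |
| 20/125 | −10 → −20 | same | −22.5 | −45 | 0 |
| 20/160 | −15 → −25 | same | **−25.0** | −45 | 0 |
| 20/200 | −20 → −30 | same | **−27.5** | −45 | 0 |
| 20/250 | −25 → −35 | same | **−25.0** | −45 | 0 |
| 20/320 | −30 → −40 | same | −22.5 | −45 | 0 |
| 20/400 | −35 → −45 | same | −22.5 | −45 | 0 |
| 20/500 | −40 → −50 | same | −22.5 | **−50** | 0 |
| 20/640 | −45 → −55 | same | −22.5 | **−55** | 0 |

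The bin is unchanged for 9 of 10 eyes. Median, minimum and maximum are all unchanged for 4 of 10 (20/100, 20/125, 20/320, 20/400). The mean moves by 10/10 = 1.0 letter in every case; for the 20/400 eye the SD goes from 15.1 to 16.3.

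**Does the SAP 7.5.1 listing capture earlier losses?** If preoperative counts among the earlier values, best prior BCDVA ≥ preoperative BCDVA in letters. Then (best prior − current) ≥ (preoperative − current), and every eye that has lost 10 or more letters from preoperative also qualifies for the listing. Its coverage is adequate; only its conditional wording limits it.

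**Reading boundary.** A change of exactly 1 minute meets the endpoint's threshold, but SAP 7.4.3 places it in the no-change bin, and the adjacent bins begin above 1 minute.

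**The case against.** The strongest reply is that the SAP already holds what is needed. The SAP 7.5.1 listing applies at each corresponding visit and is at least as sensitive as loss from preoperative. Its condition can be read as meaning that it appears whenever such an eye occurs. SAP 7.5.7.1 also promises to present all available BCDVA and does not say that its categories are exhaustive. On the ten-eye grid, the median or a range limit does move for 6 of the 10 eyes. This stands in part: the data will exist, and a careful analyst would probably show them. But the listing's condition is undefined, and neither the general presentation wording nor SAP 6.1 commits to change from preoperative.

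A reader might infer more than the documents support:
- **That the BCDVA safety endpoint itself is compromised.** It is not. The 12-month count uses letters, independently of these bins.
- **That the interim will omit BCDVA change.** SAP 6.8 lists no interim tables, so neither omission nor inclusion can be shown.
- **That summary statistics generally hide a loss.** On the assumed grid, the median, minimum and maximum together do so for 4 eyes of 10, and the grid is only an illustration.

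On reading, the unit already suggests that time was meant, the endpoint is exploratory and confined to a subset, and the clinical methods appendix is not in the reviewed text. That limits the consequence; the criterion still runs the wrong way as written.

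**Conclusion.** Both parts hold, and both should be corrected.

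The by-visit BCDVA bins cannot show a loss of two or more lines from preoperative for 10 of the 11 entry levels. Before 12 months the only output aimed at such losses is conditional. One affected eye would be at least 10% of the study. The conclusion rests on a 0.1-logMAR line. The ten-eye result also rests on an assumed spread of entry acuities, and the relevance to the 4-6 month interim is an inference.

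The reading criterion is wrong in direction if taken literally. That it was meant as reading time is likely but unconfirmed. Only an exploratory endpoint is touched; the near-acuity letter-gain endpoints are unaffected.

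The 20/40 wording for edema events in Protocol 16.3 and the uncorrected-acuity label on the exploratory subset might be read as part of the same problem. They are minor wording points and are not part of this finding.

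**What to change.** **Distance acuity**
- SAP 7.5.7.1: at each scheduled visit, tabulate change in BCDVA from preoperative on the SAP 7.4.2 letter scale (losses of more than 5, at least 10 and at least 15; within 5 either way; gains of more than 5 and at least 10, 15 and 20). Take the scale from the first bullets of 7.4.2, since its last bullet prints a loss of 20 where the others print 10. List BCDVA in letters per eye by visit.
- SAP 7.5.1: delete the words *if needed*, so that the listing of losses from best prior BCDVA is always produced.
- SAP 6.8: state that all three outputs are produced at the 4-6 month interim.

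**Reading**
- Protocol 4.5 and SAP 3.1.3 and 7.4.3: write *decrease in reading time of at least 1 minute*, once the sponsor has confirmed this against the clinical methods appendix.
- SAP 7.4.3: label the minute bins *faster* or *slower*, and align them so that a change of exactly 1 minute falls on the same side as in the endpoint.

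**Cost.** Wording edits in the SAP and in Protocol 4.5, one added table and one added listing. BCDVA is already measured from the 7-14 day visit on, so no new test or visit is needed. The downside is small counts in at most 10 eyes, which is why the per-eye listing should accompany the table.
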